Appendix 2 Food Literacy Questionnaire

1. Planning and management

14	How do you normally store your fruits and vegetables (multiple choices are possible)				
	1: In a fridge	2: On a floor in the house	3: In a basket	4: on the shelves	5: Others specify

What is your opinion on the following?

Assessment question		Likert scale				
1	What I eat has an impact on my health and wellbeing	1: Strongly Disagree	2: Somewhat disagree	3: Somewhat agree	4: Strongly Agree	
2	How often do you think about health when deciding on what to eat	1: Never	2: Rarely	3: Sometimes	4: Always	
3	Which of following food groups do you consider as a typical balanced meal	1: Matooke, Rice, Chicken, One banana	2: Matooke, Rice, Beans, One banana	3: Matooke, Rice, Greens (amaranth/managu), One banana	4: Matooke, Beans or chicken, Greens (amaranth/managu), One banana	5: Not sure
4	How often do you plan meals ahead of time?	1: Never	2: Rarely	3: Sometimes	4: Always	
5	Do you normally have plan a weekly menu?	1: Never	2: Rarely	3: Sometimes	4: Always	
6	How often do you plan the meals to include all food groups?	1: Never	2: Rarely	3: Sometimes	4: Always	
7	How easy is it for you to plan a meal including at least one food from each of the food groups on a limited budget	1: Very difficult	2: Somehow difficult	3: Somehow easy	4: Always easy	
8	How often do you think about vegetables when deciding what to eat?	1: Never	2: Rarely	3: Sometimes	4: Always	
9	How often do you think about fruits when deciding what to eat?	1: Never	2: Rarely	3: Sometimes	4: Always	

2. Questions about selection

10	How often do you make a food shopping list before going to shop?	1: Never	2: Rarely	3: Sometimes	4: Always		
11	How often do you purchase vegetables even if you have limited money?	1: Never	2: Rarely	3: Sometimes	4: Always		
12	How often do you purchase fruits, even if you have limited money?	1: Never	2: Rarely	3: Sometimes	4: Always		
13	On average how long do you stock up on the following food items						
13a	Leafy vegetables	1: Do not stock (buy for immediate consumption)	2: Daily	3: two days	4: three days	5: four to five days	6: weekly
13b	Other vegetables (carrots, cucumbers, avocado, tomatoes, eggplants etc)	1: Do not stock (buy for immediate consumption)	2: Daily	3: two days	4: three days	5: four-five days	6: weekly
13c	Fruits	1: Do not stock (buy for immediate consumption)	2: Daily	3: two days	4: three days	5: four-five days	6: weekly

3. Questions about preparation

15	How often do you cook meals at home?	1: Never	2: Rarely	3: Sometimes	4: Always
16	How often do you prepare vegetables at each main meal (e.g. pasted vegetables? a side dish)	1: Never	2: Rarely	3: Sometimes	4: Always
17	Vegetable preparation is too much work?	1: Strongly agree	2: Somehow agree	3: Somehow disagree	4: Strongly disagree
18	How confident do you feel about cooking a variety of healthy and tasty vegetables?	1: Not confident	2: Low	3: Moderate	4: High
19	How would you rate your ability to cook vegetables in at least three different ways? e.g. steaming, stir frying, pasting or in different dishes	1: Not confident	2: Low	3: Moderate	4: High
20	How often do you try out new vegetable recipes?	1: Never	2: Rarely	3: Sometimes	4: Always
21	Rate your confidence in changing recipes (written or unwritten) to make them healthier.	1: Not confident	2: Low	3: Moderate	4: High
22	How confident are you about the hygiene of home prepared vegetables?	1: Not confident	2: Low	3: Moderate	4: High
23	How confident are you that vegetables prepared at home don't contain pesticide residues	1: Not confident	2: Low	3: Moderate	4: High
24	How confident are you about the hygiene of home prepared fruits?	1: Not confident	2: Low	3: Moderate	4: High
25	How confident are you that fruits prepared at home don't contain pesticide residues	1: Not confident	2: Low	3: Moderate	4: High

4. Eating behaviours

26	How many portions of vegetables is ministry of health and world health organisation is recommending people to eat? (a portion = 3 heaped table spoons or 1 handful)	1: two or more portions a day	2: one portion a day	3: five portions a week	4: three portions a week	5: one portion a week	6: Not sure
27	How many portions of fruits ministry of health and world health organisation is recommending people to eat? (1 portion of fruit is equal to 1 medium piece of banana, orange, mango or a slice of watermelon or pineapple)	1: two or more portions a day	2: one portion a day	3: five portions a week	4: three portions a week	5: one portion a week	6: Not sure

28: Please indicate how often you consume at least one portion of fruits

1 portion of fruit is equal to 1 banana , orange, mango or a slice of watermelon or pineapple					 
What is a portion – 1 banana mango
				
1: Once in a month	2: one time a week	3: two times a week	4: three times a week	5: four times a week	6: five times a week	7: six times a week	8: one time a day	9: two or more times a day	

29: Please indicate how often you consume at least one portion of leafy vegetables

Four heaped tablespoons (one handful) of cooked green leafy veggies like cabbage, Sukuma wiki,, sagaa, managu, spinach,					 
What is a portion – 4 heaped table spoons or 1 handful
				
1: Once in a month	2: one time a week	3: two times a week	4: three times a week	5: four times a week	6: five times a week	7: six times a week	8: one time a day	9: two or more times a day	

30: Please indicate how often you consume at least one portion of vegetables other than leafy vegetables

Three heaped tablespoons (one handful) of vegetables like sliced carrots, cucumber, green pepper, eggplant, mixed vegetables					 
What is a portion – 3 heaped table spoons or 1 handful
				
1: Once in a month	2: one time a week	3: two times a week	4: three times a week	5: four times a week	6: five times a week	7: six times a week	8: one time a day	9: two or more times a day	

31	How easy is it for you to eat fruits and vegetables when you find yourself in the following situations				
31a	When at work	1: Very difficult	2: Somewhat difficult	3: Somewhat easy	4: Always easy
31b	When traveling	1: Very difficult	2: Somewhat difficult	3: Somewhat easy	4: Always easy
31c	When you experience time pressure	1: Very difficult	2: Somewhat difficult	3: Somewhat easy	4: Always easy
32	How often do you pack fruits when going to work?	1: Never	2: Rarely	3: Sometimes	4: Always
33	How often do you pack vegetables when going to work?	1: Never	2: Rarely	3: Sometimes	4: Always
34	How often do you eat vegetables as snacks (between meals)? e.g. avocado, carrots, tomatoes, cucumbers	1: Never	2: Rarely	3: Sometimes	4: Always
35	How often do you eat fruits as a snack (in between meals)?	1: Never	2: Rarely	3: Sometimes	4: Always

5. Nutrition information

36	When you have questions on what food to eat for better health, do you know where to find this information?	1: Never	2: Rarely	3: Sometimes	4: Always
37	There is a lot of information available on healthy eating today. How well do you manage to choose the information relevant to you?	1: Very difficult	2: Somewhat difficult	3: Somewhat easy	4: Always easy
38	In general, how often do you use (listen and value) the sources of nutritional information below?				
38a	Nutrition advice from family members	1: Never	2: Rarely	3: Sometimes	4: Always
38b	Nutrition advice from friends and peers	1: Never	2: Rarely	3: Sometimes	4: Always
38c	TV or radio program on nutrition	1: Never	2: Rarely	3: Sometimes	4: Always
38d	Self-proclaimed nutrition experts on streets	1: Never	2: Rarely	3: Sometimes	4: Always
38e	Health workers (doctors)	1: Never	2: Rarely	3: Sometimes	4: Always
38f	Nutritionists	1: Never	2: Rarely	3: Sometimes	4: Always
38g	Social media (WhatsApp, face book, you tube)	1: Never	2: Rarely	3: Sometimes	4: Always
39	How easy is it for you to judge if healthy eating information shared on various platforms can be trusted?	1: Very difficult	2: Somewhat difficult	3: Somewhat easy	4: Always easy

7	Which of the following describes your treatment regimen 1= insulin and oral medication only; 2= diet only; 3= insulin and diet; 4= insulin, oral medication and diet	
8	How well do you think you manage your diabetes with your eating habits? 1=Poor; 2=Fair; 3=Good; 4=Very good; 5=Excellent	

Section 3: Personal Habits and Physical Activity (Based on the STEPS Instrument (106))

Physical Activity

I am going to ask you about the time you spend doing different types of physical activity in a typical week. Please answer these questions even if you do not consider yourself to be a physically active person.

Think first about the time you spend doing work. Think of work as the things that you have to do such as paid or unpaid work, study/training, household chores, harvesting food/crops, fishing or hunting for food, seeking employment. [Insert other examples if needed].

In answering the following questions 'vigorous-intensity activities' are activities that require hard physical effort and cause large increases in breathing or heart rate, 'moderate-intensity activities' are activities that require moderate physical effort and cause small increases in breathing or heart rate.

Question	Response	Code
Work		
Does your work involve vigorous-intensity activity that causes large increases in breathing or heart rate like [carrying or lifting heavy loads, digging or construction work] for at least 10 minutes continuously? [INSERT EXAMPLES] (USE SHOWCARD)	Yes 1 No 2 If No, go to P 4	P1
In a typical week, on how many days do you do vigorous intensity activities as part of your work?	Number of days 	P2
How much time do you spend doing vigorous-intensity activities at work on a typical day?	 :  hrs mins Hours : minutes	P3 (a-b)
Does your work involve moderate-intensity activity, that causes small increases in breathing or heart rate such as brisk walking [or carrying light loads] for at least 10 minutes continuously? [INSERT EXAMPLES] (USE SHOWCARD)	Yes 1 No 2 If No, go to P 7	P4
In a typical week, on how many days do you do moderate intensity activities as part of your work?	Number of days 	P5
How much time do you spend doing moderate-intensity activities at work on a typical day?	 :  hrs mins Hours : minutes	P6 (a-b)
Travel to and from places		
The next questions exclude the physical activities at work that you have already mentioned		
Now I would like to ask you about the usual way you travel to and from places. For example to work, for shopping, to market, to places of worship. [Insert other examples if needed]		
Do you walk or use a bicycle (pedal cycle) for at least 10 minutes continuously to get to and from places?	Yes 1 No 2 If No, go to P 10	P7
In a typical week, on how many days do you walk or bicycle for at least 10 minutes continuously to get to and from places?	Number of days 	P8

How much time do you spend walking or bicycling for travel on a typical day?	Hours : minutes  :   hrs  mins	P9 (a-b)
Question	Response	Code
Recreational activities		
The next questions exclude the work and transport activities that you have already mentioned. Now I would like to ask you about sports, fitness and recreational activities (leisure), [Insert relevant terms].		
Do you do any vigorous-intensity sports, fitness or recreational (leisure) activities that cause large increases in breathing or heart rate like [running or football] for at least 10 minutes continuously? [INSERT EXAMPLES] (USE SHOWCARD)	Yes 1 No 2 If No, go to P 13	P10
In a typical week, on how many days do you do vigorous intensity sports, fitness or recreational (leisure) activities?	Number of days 	P11
How much time do you spend doing vigorous-intensity sports, fitness or recreational activities on a typical day?	Hours : minutes  :   hrs  mins	P12 (a-b)
Do you do any moderate-intensity sports, fitness or recreational (leisure) activities that cause a small increase in breathing or heart rate such as brisk walking, [cycling, swimming, volleyball] for at least 10 minutes continuously? [INSERT EXAMPLES] (USE SHOWCARD)	Yes 1 No 2 If No, go to P16	P13
In a typical week, on how many days do you do moderate intensity sports, fitness or recreational (leisure) activities?	Number of days 	P14
How much time do you spend doing moderate-intensity sports, fitness or recreational (leisure) activities on a typical day?	Hours : minutes  :   hrs  mins	P15 (a-b)
Sedentary behaviour		
The following question is about sitting or reclining at work,t home, getting to and from places, or with friends including: sitting at a desk, sitting with friends, traveling in car, bus, train, reading. playing cards or watching television, but do not include sleeping. [INSERT EXAMPLES] (USE SHOWCARD)		
How much time do you usually spend sitting or reclining on a typical day?	Hours : minutes  :   hrs  mins	P16 (a-b)

Section 4: Food Consumption

24-Hour Recall Questionnaire

Please write down all foods and beverages consumed for the previous 24-hour time (one day) period starting at 12:00 am and ending at 11:59 pm.

List the approximate Time the meal was consumed, Place where it was consumed (home, work, name of restaurant, church, etc.), and the type of eating occasion or Meal (breakfast, lunch, dinner, snack, or other). List each Food/Beverage Item you consumed, including foods eaten between meals and all drinks, even if it is a non-caloric item like water, coffee, or tea. Specify Details/Ingredients/Preparation of each food or beverage consumed. Record the Amount of each food or beverage consumed using weight (grams, kilograms) and volume (millilitres, litres). Cups, tablespoons, and teaspoons measures can also be used. Size (small, medium, large, length, width, height) measures the physical dimensions or proportion of a food.

Date of interview:

Date of Record:

Meal & Time	Place	Food/Beverage Item	Details/Ingredients/Preparation	Amount
Breakfast				
Midmorning snack				
Lunch				
Afternoon snack				
Dinner				
Night snack				

Would you consider the above two intake records of foods and beverages today a typical day's eating pattern?

1= Yes; 2=No

If no, explain why not typical?

Section 5: Anthropometric Measurements

S/N	Measure	1 st reading	2 nd reading	Average
1	Weight (kg)			
2	Height (m)			
3	Triceps skin fold thickness (mm)			
4	Waist circumference (cm)			
5	Hip circumference (cm)			
6	Body composition measurement

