6.2 Participants

6.2.1 *Setting of the study*

This study will be conducted in Nakuru County, located 157km North-West of Nairobi, Kenya (Appendix 1). Nakuru County covers an area of 7,495 km² and has 11 administrative Sub-Counties including Nakuru Town East, Nakuru Town West, Naivasha, Molo, Gilgil, Njoro, Kuresoi North, Kuresoi South, Rongai, Nakuru North and Subukia (98). The county is estimated to have a population of nearly 2 million people (99) and an estimated prevalence of 2.4% of type 2 diabetes among adults aged ≥50 years (6).

6.2.2 *Inclusion and exclusion Criteria*

Participants will be eligible for inclusion into the study if they meet the following criteria:

- a. adults over the age of 18 years;
- b. diagnosed the type 2 diabetes within the previous 1 year and obtaining care at a participating level 4 hospital;
- c. able to read English or Swahili Language (self-reported).
- d. currently own and able to read and send mobile text messages using any phone;

Participants will be excluded if they:

- a) are on dialysis;
- b) are pregnant;

- c) are unable to use mobile phone because of mental or visual impairment or any other reason.

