6.8.2 Control group

The control group will continue receiving standard care in the hospitals. The control group shall receive a reminder text messages one day before the routine clinic appointment. The clinic appointment dates shall be derived from the hospital where the participant receives routine diabetes care.

Figure 3 describes the study timeline and workflow. At the beginning of the intervention, both the control and intervention groups will receive introductory text messages. Text messages shall consist of personalized salutation (using the preferred name of the participant) sent to the officially registered mobile numbers. The messages shall be sent between 10am and 3pm through the Africa’s Talking® Application Programming Interface (API).

[figure not shown]

Figure 3. Study timeline

Table 2. Text messages for specific target behaviors

COM-B Components	What needs to happen for the target behavior to occur?	Behavior Change Technique	Text No	Text Messages	
Physical capability	Be able to select healthy food	Instructions on how to perform behavior	S 1	To meet nutrient needs within calorie limits, choose a variety of nutrient-dense foods across and within all food groups in recommended amounts. Energy dense foods include vegetables, fruits, whole grains, beans, nuts and seeds, and lean protein — when prepared with little or no saturated fats, added sugars and sodium	
			S 2	There are 5 food groups: (1)Vegetables and legumes or beans (2)Fruit; (3)Lean meats and poultry, fish, eggs, nuts and seeds, legumes or beans;(4) Grain (cereal) foods, mostly wholegrain or high cereal fiber varieties (5) Milk, yoghurt, cheese or alternatives, mostly reduced fat.	
			S 3	Reduce foods and beverages that are high in added sugars to better control your blood sugar. To avoid added sugars, check for words like brown sugar, corn sweetener, corn syrup, dextrose, fructose, and high-fructose corn syrup. These are added sugars	
			S 4	Reduce or avoid foods and beverages that are high in saturated fat like whole milk, cream, butter, cheese, meat, palm oil and coconut oil. Instead, select low-fat milk and use healthier plant-based oils.	
			S 5	Instead of selecting canned fruit or bottled juices, buy fresh juice or fruits as they are energy dense and have fiber that helps in blood sugar control. Fresh fruits are also cheaper.	

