6.9.2 Secondary Outcome measures

Secondary outcome measures will include biochemical, anthropometric and behaviour change measurements shall be measured at baseline and endline (end of week 12). Additionally, user-satisfaction shall be assessed at 12 weeks and 24 weeks post-intervention.

Biochemical measurements will include fasting plasma Glucose (FPG), total cholesterol (TC), triglycerides (TG), and high-density lipoprotein-cholesterol (HDL-C). FPG will be analysed by the glucose oxidase method using a Hitachi 7600, while TC, TG, HDL-C will be measured using the automatic blood analyser (Hitachi 736-40). Lab testing and analysis will be conducted at the Lancet laboratories, Kenya using standard procedures.

Anthropometric measurements will include weight, height, waist and hip circumferences that shall be measured by trained research assistants, and shall follow the CDC Anthropometry Procedures Manual (104). Additionally, bioelectrical impedance analysis shall be taken to determine body fat using the

Behaviour change shall be measured by changes in dietary intake of legumes, fruits and vegetables and through the mHealth Satisfaction Questionnaire (Appendix 6). The mHealth Satisfaction Questionnaire will be adopted from the questionnaire for assessing user satisfaction with mobile health apps (105).

7 Data Collection

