7.1 Quantitative Instruments

Various tools will be used to collect data. The socio-demographic and health questionnaire (Appendix 3), the food frequency questionnaire (Appendix 4) and the self-perceived food literacy questionnaire (Appendix 5) will be administered on all participants after enrolment. The socio-demographic and health questionnaire and the food frequency questionnaires have been piloted and used in studies in Kenya, while the self-perceived food literacy questionnaire shall be piloted during the study. These tools will be administered by trained research personnel in either Swahili or English, depending on the preference of the participant.

7.1.1 *Socio-demographic and health history questionnaire*

This study will utilize the electronic socio-demographic and health history questionnaire (Appendix 4) that was previously used in a sister study conducted in Makueni County, Kenya (Protocol number AMREF P424 2018). The questionnaire was developed based on the World Health Organization STEPS Instrument and Support Materials (106) and piloted in Makueni County, Kenya.

7.1.2 *Self-perceived food literacy questionnaire*

The self-perceived food literacy questionnaire is based on the tool used to assess the food literacy among people with chronic diseases in Netherlands (107). This tool was developed through an expert-based and theory-driven process and shall be piloted and adjusted before being used in the Kenyan settings. The responses options are a 5-point Likert scale where 1= 'not at all/never' to 5='yes/always' (Appendix 4).

7.1.3 *Anthropometric measurements*

Anthropometric measurements will be taken during the filling of the socio-demographic and Health history questionnaire. These measurements will include height, weight waist and hip circumference. Height and weight shall be used to calculate the body mass index (BMI).

7.1.4 *Body composition*

Body composition of all participants shall be taken at baseline and at the end of the intervention. The measurements shall be conducted by trained research assistants using the *Bodystat 500*[®] Body Composition Monitor.

7.1.5 *Blood samples*

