8.2 Plan for analysis of quantitative data

Quantitative data will be analyzed by the intention to treat principle (115). Various patient characteristics and primary outcome measures, including anthropometric and biochemical measurements (HbA1c, FBG, lipid profiles) at baseline will be summarized using descriptive statistics. The descriptive statistics will include means and standard deviations for continuous variables and proportions for categorical variables.

HbA1c levels will be compared at 3-months between the two arms using an ANCOVA which will control for baseline HbA1c levels. The intervention and the control groups will be followed-up for six months. One-way and interactive text messaging data will be analyzed descriptively.

A subgroup analyses per hospital and participant socio-demographics including age, sex, education, and income levels will be conducted. All statistical analyses will be performed using R version 4.0.3 (116).

9 Plan for communicating findings of the study

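### Item 7 of the health history questionnaire has no code for oral medication only, oral medication with diet, or insulin only, so the baseline treatment description would be wrong

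*Protocol*

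**What the plan says.** The response list for item 7 reads "1= insulin and oral medication only; 2= diet only; 3= insulin and diet; 4= insulin, oral medication and diet". The codes run from 1 to 4 without a gap, and no category for other regimens is shown.

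Section 7.1 says that this questionnaire, with the food frequency and food literacy questionnaires, "will be administered on all participants after enrolment". Under the same heading, 7.1.3 links it to the physical measurements: "Anthropometric measurements will be taken during the filling of the socio-demographic and Health history questionnaire". Section 6.9.2 says that the secondary outcomes, anthropometry among them, "shall be measured at baseline and endline (end of week 12").

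On who may enter, section 6.2.2 requires that a participant be "diagnosed the type 2 diabetes within the previous 1 year and obtaining care at a participating level 4 hospital". The exclusions are dialysis, pregnancy and inability to use a phone; no drug regimen is excluded. Section 6.8.2 adds: "The control group will continue receiving standard care in the hospitals".

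On analysis, section 8.2 begins with "Various patient characteristics and primary outcome measures", to be summarised at baseline, with proportions for categorical variables. The primary comparison is an ANCOVA of HbA1c at 3 months, adjusted for baseline HbA1c. The subgroups are hospital, age, sex, education and income. Treatment regimen is in neither.

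**The concern.** A closed list must have a place for every eligible participant. This one has no place for anyone who takes oral medication without insulin, or insulin without a dietary component. The interviewer then has to choose a false code or leave the item blank. Two interviewers may choose differently, and the data set will not show which did what.

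Two things are at stake. The first is the baseline table: treatment regimen is a patient characteristic of obvious interest in a trial whose endpoint is HbA1c, and its proportions would be wrong. The second is interpretation. The hypothesis in section 5 is that messages act through food literacy and dietary behaviour. A reader of the results will want to see, by arm, what glucose-lowering treatment participants were on at the start and at week 12. An item that cannot describe common combinations does not allow this, however often it is asked. No analysis plan can recover an answer that the form never offered.

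**Working it through.** **Inputs.** The response list of item 7; the eligibility criteria in 6.2.2; the sample size of 60 (30 per arm) in 6.3. The plan states no figure on this point that could be reproduced, so the check is an enumeration.

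**Step 1: all combinations.** Three components, each present or absent and at least one present, give 2³ − 1 = 7 regimens.

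| Regimen | Code in item 7 |
|---|---|
| Diet only | 2 |
| Oral only | none |
| Insulin only | none |
| Oral + diet | none |
| Insulin + diet | 3 |
| Insulin + oral | 1 |
| Insulin + oral + diet | 4 |

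Four of seven have a code and 7 − 4 = 3 have none. Both regimens with oral medication but no insulin are among the three.

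**Step 2: a more generous reading.** Suppose that diet is taken for granted and only drug treatment matters. There are then four states: no drug (code 2), insulin alone (code 3), both (codes 1 and 4) and oral medication alone (no code). On this reading the insulin-only gap disappears. The oral-medication gap does not.

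**Step 3: can such participants enter?** Yes. Section 6.2.2 sets a limit on time since diagnosis and none on drug regimen.

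**Step 4: how many records?** If a share *p* of participants is on an uncoded regimen, the number of wrong or blank records is 60 × *p*. The documents do not give *p*. Each 10 percentage points is 60 × 0.10 = 6 records. As an assumption only, *p* between 0.50 and 0.80 gives 60 × 0.50 = 30 to 60 × 0.80 = 48 records.

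**Step 5: which planned results use the item?** The baseline summary in 8.2 is the only one that the text supports. Section 8.2 does not name regimen, but regimen is a categorical patient characteristic collected on the baseline form. The primary ANCOVA and the listed subgroups do not use it.

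**Step 6: when is it asked?** Section 7.1 places the form after enrolment and states no repeat. Anthropometry is measured at baseline and week 12, is taken while this form is completed, and is section 5 of the form as printed. The form may therefore be opened again at week 12, but the text does not settle whether item 7 is then asked again.

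**The case against.** The strongest reply is that this is a descriptive item in a 60-person proof-of-concept trial and enters no specified comparison. That stands. The primary estimate does not depend on item 7, and the consequence is confined to description and interpretation.

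The pages just before item 7 are not in the public copy, and an earlier item may record drugs. That also stands as a limit: it cannot be said that the trial as a whole will misclassify treatment. It does not rescue item 7. If an earlier item does record drugs, item 7 will conflict with it for every participant on an uncoded regimen.

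A reader might go further and infer that treatment is recorded once, at enrolment, so that later drug changes cannot be seen. The documents do not say so. Section 7.1 does not limit the form to one occasion, and the same sentence covers the food literacy questionnaire, whose score is meant to increase under the specific objectives in 3.5 and so must be measured again. The link with anthropometry also points to reuse at week 12.

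A reader might also infer that unrecorded drug changes bias the HbA1c comparison, and try to put a size on this. Under intention to treat, drug changes after randomisation are part of what follows from assignment. They do not bias the effect of assignment; they limit how far a difference can be attributed to the dietary messages. Any figure for the shift would be a product of assumed inputs that the documents do not contain.

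**Conclusion.** The point holds as an error in a stated instrument. Three of the seven possible regimens have no code, and oral medication without insulin has none even on the most lenient reading. Eligible participants on these regimens must be miscoded or left blank, and the regimen proportions in the baseline description would be wrong. The number of records depends on the share of participants on those regimens, which the documents do not give.

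The primary intention-to-treat ANCOVA is not affected. The conclusion concerns item 7 as printed; it does not rest on what the unseen items contain or on how often the form is used. It is a modest but definite defect, worth correcting before fieldwork because it cannot be reliably repaired afterwards.

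**What to change.** Replace item 7 with three yes/no items: insulin; oral glucose-lowering medication; diet. Together they record all seven combinations. Adding the three missing codes to the present list would also do. Make the change before the pilot of this questionnaire described in section 7.2, so that the corrected wording is what is piloted.

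State in section 7.1 that the corrected item is completed at baseline and again at the week-12 visit, when anthropometry is already taken with this form. Tabulate the answers by arm at both times, so that a difference in HbA1c can be read alongside treatment. These items show classes of treatment and not drug or dose, so the table supports interpretation without explaining a difference fully.

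The primary analysis needs no change. A further ANCOVA adjusted for baseline regimen is not proposed, since it would not address changes after randomisation.

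The cost is a small edit to an electronic form and about a minute per visit.
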